4.3.2.2. ITT Part 1 Interim

ITT Part 1 interim set included all patients who were randomly assigned to a study drug prior to the conclusion of Part 1 of the study and were included in the interim analysis. Patients will be analyzed according to the treatment they were randomly assigned to.

4.3.2.3. ITT Part 2

The ITT Part 2 Set includes all patients who were randomly assigned to a study drug after the conclusion of Part 1 of the study and patients enrolled during the interim analysis on placebo and the selected optimal recAP dose group. This analysis set will be used to compare patients enrolled during the different parts of the study. Patients will be analyzed according to the treatment they were randomly assigned to.

4.3.3. Per Protocol

Analysis on the PP Set will be used as a supplement to the ITT analysis and will be performed for the primary efficacy and key secondary endpoint described as follows:

4.3.3.1. PP Day 1 – 7 Combined

The PP Day 1 – 7 Combined Set includes all patients who were randomly assigned to a study drug in either Part 1 or Part 2 of the study, had no significant protocol deviations (PDs) (e.g. non-adherence to inclusion/exclusion criteria with enrollment of the patient, or non-adherence to FDA regulations or ICH E6(R1) guidelines) and had complete data

(meaning no more than two missing day 1-7 creatinine clearance values) for the primary endpoint. The primary endpoint will be analyzed for the PP Day 1-7 Combined Set, with patients analyzed according to the treatment they received. See Section 10.2.2 of the protocol and the Significant Protocol Deviation Rules document for further information on the handling of PDs for this study. Significant PDs will be identified prior to study unblinding and summarized by the deviation categories specified above.

4.3.3.2. PP Day 1 – 7 Part 1

The PP Day 1 – 7 Part 1 Set includes all patients who were randomly assigned to a study drug prior to the conclusion of Part 1, excluding patients enrolled during the interim analysis on placebo and the selected optimal recAP dose group and are included in the ITT Part 1 Interim Set, had no significant protocol deviations (PDs) (e.g. non-adherence to inclusion/exclusion criteria with enrollment of the patient, or non-adherence to FDA regulations or ICH E6(R1) guidelines) and had complete data (meaning no more than two missing day 1-7 creatinine clearance values) for the primary endpoint. The primary endpoint will be analyzed for the PP Day 1-7 Part 1 Set, with patients analyzed according to the treatment they received. See Section 10.2.2 of the protocol and the Significant Protocol Deviation Rules document for further information on the handling of PDs for this study. Significant PDs will be identified prior to study unblinding and summarized by the deviation categories specified above.

4.3.3.3. PP Day 1–7 Part 2

The PP Day 1–7 Part 2 Set includes all patients who were randomly assigned to a study drug after the conclusion of Part 1 of the study, including patients enrolled during the interim analysis on placebo and the selected optimal recAP dose group, had no significant PDs (e.g. non-adherence to inclusion/exclusion criteria with enrollment of the patient, or non-adherence to FDA regulations or ICH E6(R1) guidelines) and had complete data (meaning no more than two missing day 1-7 creatinine clearance values) for the primary endpoint. The primary endpoint will be analyzed for the PP Day 1-7 Part 2 Set, with patients analyzed according to the treatment they received. See Section 10.2.2 of the protocol and the Significant Protocol Deviation Rules document for further information on the handling of PDs for this study. Significant PDs will be identified prior to study unblinding and summarized by the deviation categories specified above.

4.3.4. Safety

The Safety Set includes all patients who were randomly assigned and received a dose of study drug. All safety analyses will be based on the Safety Set, with patients analyzed according to the treatment they received.

4.3.5. Pharmacokinetics (PK)

The PK Set includes all patients who were randomly assigned and received at least one treatment during Part 1 of the study. The PK analyses will be based on this set, with patients analyzed according to the treatment they received.

4.3.6. Iohexol

The Iohexol Set includes all patients who were administered iohexol.

5. Patient Disposition

5.1. Disposition

Patient disposition will be summarized for the all Enrolled Set. A disposition of patients includes the number and percentage of patients for the following categories: patients who were not randomly assigned to treatment, patients in the ITT Combined Set, patients treated (Safety Set), patients in the PP Day 1-7 Combined Set, patients in the PP Day 1-7 Part 1 Analysis Set, patients in the ITT Part 1 Set, patients in the ITT Part 1 Interim Set, patients in the ITT Part 2 Set, patients in the PP Day 1-7 Part 2 Set, patients in the PK Set and patients in the Iohexol Set. The number and percentage of patients who completed the study and patients who discontinued from the study will be summarized for the ITT Combined Set, the ITT Part 1 Set, ITT Part 1 Interim Set and the ITT Part 2 Set. The percentages will be based on the number of patients in each analysis set.

The reasons for study discontinuation will also be summarized in this table. The reason for study discontinuation includes the following: Adverse Event, Lab abnormality, Patient Withdrew consent, Investigator Decision, Sponsor termination of study, Protocol Non-Compliance or violation, Death and Other. The percentages will be based on the number of patients who discontinued from the study.

The disposition table will be repeated by site for the all Enrolled Set.

Patient disposition data will be presented in a listing.

5.2. Screen Failures

All patients who are screen failures will be presented in a listing for the all Enrolled Set, together with the reason for failing screening.

5.3. Protocol Deviations

All PDs will be recorded throughout the study (recorded on the clinical trial management system), and reviewed on an ongoing basis. Significant PDs will be identified according to the Significant PD Rules for the study, and presented in a listing for the all Enrolled Set.

6. Demographics and Baseline Characteristics

6.1. Demographics

A summary of demographics and baseline information will be presented for the ITT Combined Set, ITT Part 1 Set and ITT Part 2 Set. The demographic characteristics consist of age (years), sex and race. Baseline weight can be recorded on the eCRF at screening in either kg or lb, weight in lb will be converted to kg using the calculation in [Section 4](#). Baseline weight (kg), baseline height (cm), and body mass index (BMI) (kg/m^2) will be included in the summary.

A patient's age in years will be calculated using the date of the informed consent and date of birth. Age (years) and baseline weight (kg) will be summarized using descriptive statistics. The number and percentage of patients by age category (<55 , $\geq 55 - < 70$, ≥ 70), sex (Male, Female) and race (Caucasian, Black, Asian, Other and Not Collectable), will also be reported. Not Collectable category is available as race is not allowed to be collected in certain countries.

Patient demographic and baseline characteristics will be presented in a listing based on the ITT Combined Set.

6.2. Baseline Disease Characteristics

The distribution of patients across treatment groups will be presented for the following characteristics. This will be in the form of descriptive statistics for continuous data, or as the number and percentage of patients included in each category for categorical data. This summary will be presented for the ITT Combined Set, and also for the ITT Part 1 Set and ITT Part 2 Set to check the assumption that patients recruited in each part of the study will belong to the same overall patient population. This will include:

- Fractional excretion of sodium and fractional excretion of urea summarized by descriptive statistics;
- eGFR by CKD-EPI by descriptive statistics;
- SAPS-2 by descriptive statistics;
- SOFA score by descriptive statistics;

- Alkaline Phosphatase activity by descriptive statistics;
- The number and percentages of patients by mechanical ventilation at baseline categories (yes, no);
- The number and percentages of patients by infectious agent categories (yes, no);
- The number and percentages of patients by AKI stage (stage 1, stage 2, stage 3) according to the AKIN criteria;
- Heart rate by descriptive statistics;
- Systolic blood pressure by descriptive statistics;
- Diastolic blood pressure by descriptive statistics;
- The number and percentages of patients by body temperature categories ($<36^{\circ}\text{C}$, $\geq 36^{\circ}\text{C}$ to $\leq 38^{\circ}\text{C}$ and $>38^{\circ}\text{C}$);
- Urine output by descriptive statistics;
- Serum creatinine at baseline from the central laboratory data by descriptive statistics; values will be converted to mg/dL; if baseline central laboratory data is unavailable, but there is local laboratory measured serum creatinine available for the subject, then the baseline value obtained by the local laboratory will be used;
- Creatinine clearance (using the formula given in 8.1 to derive the measured value) by descriptive statistics;
- Acute physiology and chronic health evaluation (APACHE) II score by descriptive statistics and by frequency count (<25 vs. ≥ 25);
- The number and percentages of patients with vasopressor/inotropic therapy use at baseline (yes, no)

The baseline disease characteristics and microbes specified for infectious agents, for all patients in the ITT Combined Set will also be presented in a listing.

6.3. Medical History

Medical history is collected at screening and will be coded using the Medical Dictionary for Regulatory Activities (MedDRA) Version 16.1 or later. The number and percentage of patients with any medical history will be summarized overall and for each system organ class (SOC) and preferred term (PT) for the ITT Combined Set. At each level of patient summarization, a patient is counted once.

Patient medical history data including specific details will be presented in a listing.

6.4. Inclusion and Exclusion Criteria

A listing, based on the all Enrolled Set, will be included displaying which protocol version/amendment each patient was recruited under, and whether the patient met and/or did not meet the inclusion and exclusion criteria.

7. Treatments and Medications

7.1. Concomitant Medications

Concomitant medications will be collected throughout the study and coded using the latest version of World Health Organization (WHO) Drug in use at the time of coding. The total number of concomitant medications and the number and percentages of patients with at least one concomitant medication will be summarized by treatment group. The number and percentages of all concomitant medications will be summarized by treatment group and listed by drug class and PT. At each level of patient summarization, a patient is counted once.

All summaries will be performed using the Safety Set.

Patient concomitant medication data including specific details will be presented in a listing.

7.2. Study Treatments

RecAP is supplied as a clear, colorless, pyrogen-free solution in 10 mL type 1 glass vials. Each vial contains 5 mL of recAP solution. Matching placebo is supplied as a clear, colorless, pyrogen-free solution in 10 mL type 1 glass vials. Each vial contains 5 mL of placebo solution.

Patient doses will be prepared from 4 vials in a combination of recAP drug product and recAP placebo. The content of the 4 vials will be used to fill an IV dosing syringe (50 mL) with an appropriate volume corresponding to the body weight of the patient, followed by addition of physiological saline solution to a total of 50 mL.

7.2.1. Extent of Exposure

The number and percentages of patients that received any dose on Day 1, Day 2 and Day 3 will be summarized by treatment group. The number and percentages of patients will also be presented by total number of doses received (1 dose, 2 doses, 3 doses) by treatment group. All summaries will be performed using the Safety Set. The number and percentage of patients who discontinued the study prior to receiving treatment on Day 1, Day 2 and Day 3 will also be included.

Study Drug Infusion information will be presented in the form of a listing for the Safety Set, including: was patient dosed (Yes, No); infusion start time; infusion end time; route of

administration (central line, peripheral line); volume of all 4 vials drawn into the 50 mL syringe (yes, no); volume from the 4 vials discarded from the syringe based on patients weight (mL); saline added to the 50 mL syringe (mL), was total volume of 50 mL syringe administered (yes, no), and, if no, reason why total volume was not administered; and total volume of study drug administered (mL).

8. Efficacy Analysis

A hierarchical method will be employed to address any multiplicity arising from the analysis of the key secondary endpoint. In other words, the formal analysis of this endpoint will be performed only if a statistically significant result is obtained from the combination test analysis of the primary endpoint. All analyses performed on the other secondary endpoints are for exploratory purposes only; therefore, no further multiplicity adjustment is required. The results of this hierarchical method will be presented indicating where statistically significant results are obtained.

To provide an overall summary of the efficacy analyses, a table will be produced containing the results and magnitude of difference between the optimal recAP dose and placebo treatment groups for certain key endpoints. This table will be based on the ITT Combined Set.

Supportive analysis will be undertaken on a selection of endpoints (AUC_{1-7} and RRT incidence from Day 1 to Day 28, inclusive) including specific group categories as factors to assess the consistency of treatment effects.

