3.1. Overall Study Design and Plan

This is a randomized, double-blind, placebo-controlled, 4-arm, parallel-group, proof-of-concept, and dose-finding adaptive Phase 2a/2b study.

Approximately 290 patients with SA-AKI will be enrolled in the study. The study involves 2 parts (Part 1, Part 2) with an interim analysis between the parts, with some recruitment during this interim analysis. Of the 290 planned patients, at least 120 patients will enroll in Part 1 and 170 patients will enroll in Part 2. Patients enrolled during Part 1 will be randomly assigned to receive, by 1-hour intravenous (IV) infusion, either placebo ($n_1 = 30$) or 1 of 3 different doses of recAP ($n_1 = 30$ in each dosing arm; i.e., 0.4 mg/kg [250 U/kg], or 0.8 mg/kg [500 U/kg], or 1.6 mg/kg [1000 U/kg]) using a 1:1:1:1 allocation ratio. Patients will receive study drug once daily for 3 days (Days 1, 2, and 3). The interim analysis on the primary endpoint will be performed after 120 patients have completed the first 7 days in Part 1 (allowing for patients that were randomized but discontinued/died prior to 7 days) and all relevant data have been monitored to select the dose to be administered in Part 2. The dose chosen will be the most optimal dose of recAP on the primary endpoint in Part 1, provided there are no safety issues with that dose as judged by the DMC. While the intention is to choose the optimal recAP dose based on the primary efficacy endpoint results for Part 1, it is possible that this dosing group will have adverse safety issues. In this case, the next “best” dose with supportive safety data would be chosen for Part 2.

In Part 2, patients will be randomly assigned to receive either placebo ($n_2 = 85$) or the dose of recAP ($n_2 = 85$) selected during the interim analysis.

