4.1. Sample Size

A sample size of $n_1 = 30$ patients per treatment group in Part 1 with an additional $n_2 = 85$ patients recruited to each of the optimal recAP dose and placebo treatment groups in Part 2 (for a total sample size of $n = 290$ patients) is planned. Recruitment will continue during the interim analysis, so the total number of patients will exceed 290. Custom programmed simulations were performed using SAS[®] Version 9.2 (SAS Institute, Inc, Cary, North Carolina) to determine power and type I error rate of the chosen sample size and design under a number of different dose response scenarios. Each scenario assumed a standard deviation of 49 mL/min for the primary endpoint (area under the time-corrected endogenous creatinine clearance curve from Day 1 to Day 7 [AUC₁₋₇]) with an assumed response of 60 mL/min for the placebo group, and between 60 mL/min (no treatment effect) and 79 mL/min (strong treatment effect) for the recAP dose groups.

Fifty-thousand simulations were performed to show that the 1-sided type I error rate is 2.4% (and hence is well controlled at the 1-sided 2.5% significance level). The power was defined as the probability of rejecting the null hypothesis (of no difference between treatment groups) when 1 or more recAP dose groups have an effective treatment effect, defined as a response of 69.5 mL/min. This was investigated across 7 scenarios with 10 000 simulations performed for each. In the most realistic scenarios (with strong treatment effects, i.e., responses of 79 mL/min for the medium and high recAP dose groups and a varying response of between 60 mL/min and 79 mL/min for the low-dose group) the chosen design achieved power of between 79% and 86%. This dropped to 66% to 67% for other scenarios where only the high recAP dose group had a strong treatment effect.

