4.3.2. Intent-to-Treat Combined

The Intent-to-Treat (ITT) Combined Set includes all patients who were randomly assigned to a study drug in either Part 1 or Part 2 of the study, excluding patients recruiting whilst the interim analysis is performed to treatment arms not selected for Part 2. This is the primary analysis set for the efficacy analyses, and patients will be analyzed according to the treatment to which they were randomly assigned.

4.3.2.1. ITT Part 1

The ITT Part 1 Set includes all patients who were randomly assigned to a study drug prior to the conclusion of Part 1 of the study excluding patients enrolled during the interim analysis on placebo and the selected optimal recAP dose group (these patients will be included in Part 2 of the study). This analysis set will be used to compare patients enrolled during the different parts of the study. Patients will be analyzed according to the treatment they were randomly assigned to.

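### The overall efficacy summary table reports the selected dose's effect on data that include the patients used to select it, with no adjustment or label, although a selection-free Part 2 estimate is already planned

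*SAP*

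**What the plan says.** SAP Section 8 (Efficacy Analysis) plans one table as an overall summary of efficacy. It is to hold the results and the "magnitude of difference between the optimal recAP dose and placebo treatment groups for certain key endpoints", and "This table will be based on the ITT Combined Set". The endpoints are not listed and no confidence interval is mentioned.

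SAP Section 4.3.2 says that the ITT Combined Set "includes all patients who were randomly assigned to a study drug in either Part 1 or Part 2 of the study". It leaves out only patients recruited during the interim analysis to doses that were then dropped. The Part 1 patients analysed at the interim therefore belong to it.

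Those same patients determine the dose. SAP Section 3.1: "The dose chosen will be the most optimal dose of recAP on the primary endpoint in Part 1", subject to the DMC's view of safety.

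For the primary endpoint, SAP Section 8.1.1 reports least squares means, their difference and a 95% interval separately for the Part 1 interim analysis and for Part 2. The combined result is a one-sided p-value from the inverse normal combination test, with Dunnett-adjusted Part 1 p-values for the intersection hypotheses. No combined estimate or interval is defined there. Models fitted to the pooled ITT Combined Set do appear as sensitivity and supportive analyses of AUC1-7 (Sections 8.1.4 and 8.1.5) and as the specified analysis of RRT incidence (Section 8.2.1).

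**The concern.** The arm with the best Part 1 mean will, on average, have been lucky in Part 1. The closed combination test allows for this in the primary p-value. A pooled difference does not: it carries the Part 1 luck, diluted by Part 2. The cautions in SAP Section 4 and Protocol Section 7.7 about combining the parts concern differences in population and in treatment effect, not selection.

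A primary objective is to find the dose or doses that support the Phase 3 program, and the overall table is a natural place to look for an effect size. Required sample size varies as 1/effect². A planner who took the pooled value at face value when the true effect is 19 mL/min would, on the average bias, size the trial at (19/20.98)² = 0.82 of what is needed in the worst case (18% short), or (19/19.75)² = 0.93 in the mildest (7% short).

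**Working it through.** **Inputs** (all from SAP Section 4.1, repeated in Protocol Section 7.4)

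- Sizes: "A sample size of $n_1 = 30$ patients per treatment group in Part 1 with an additional $n_2 = 85$ patients" for each of the selected dose and placebo. Pooled n = 115 per arm; Part 1 share 30/115 = 26%.
- Spread: "Each scenario assumed a standard deviation of 49 mL/min for the primary endpoint".
- Means: "with an assumed response of 60 mL/min for the placebo group, and between 60 mL/min (no treatment effect) and 79 mL/min" for the recAP groups, so an effect of 0 to 19. An effective dose is one said to "have an effective treatment effect, defined as a response of 69.5 mL/min", an effect of 9.5.

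**Model.** Select the recAP arm with the largest Part 1 mean. Stop if all three one-sided p-values exceed 0.8. Run Part 2 with 85 per arm. Apply the closed inverse normal test with weights √(30/115) and √(85/115), using Dunnett p-values for the two- and three-dose intersections and critical value 1.96. There were 400,000 simulated trials per scenario (1,000,000 under the null). The pooled estimate is the 115 versus 115 mean difference with an ordinary t-based 95% interval.

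**Step 1: reproduce the plan's figures.** The SAP gives power of 79-86% with the medium and high doses at 79, 66-67% when only the high dose has a strong effect, and one-sided type I error of 2.4%.

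**Step 2: bias and coverage of the pooled difference**, from the same runs:

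| Low/mid/high (mL/min) | Rejection rate | Bias (mL/min) | Two-sided coverage | Lower limit above truth | Upper limit below truth |
|---|---|---|---|---|---|
| 60/79/79 | 81.5% | +1.45 | 94.9% | 3.8% | 1.3% |
| 69.5/79/79 | 79.2% | +1.72 | 94.6% | 4.2% | 1.2% |
| 79/79/79 | 85.5% | +1.96 | 94.6% | 4.5% | 1.0% |
| 60/69.5/79 | 67.2% | +1.21 | 94.8% | 3.7% | 1.5% |
| 69.5/69.5/79 | 65.7% | +1.56 | 94.7% | 4.0% | 1.2% |
| 60/60/79 | 69.5% | +0.75 | 94.9% | 3.2% | 1.9% |
| 60/60/60 | 2.5% | +1.98 | 94.6% | 4.4% | 1.0% |

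The power ranges are reproduced. The 60/60/79 row lies somewhat above 66-67%, but the SAP does not list its seven scenarios. The model is therefore close to the sponsor's. Bias and coverage count all trials. Under the null 5.0% stop for futility, and among those that continue the bias is +2.29.

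**Step 3: analytic check with equal doses.** The expected maximum of three standard normals is 0.846.

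- Part 1 bias: 0.846 × 49/√30 = 7.57 mL/min.
- Pooled bias: 7.57 × 30/115 = 1.98 mL/min.
- Pooled SE: 49 × √(2/115) = 6.46, so the maximum bias is about 0.31 SE.
- Against an effect of 19: 0.75/19 = 4% to 1.98/19 = 10%.

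Coverage hardly moves because selection also narrows the distribution of the chosen arm's Part 1 mean. The misses shift to one side instead.

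**Step 4: Part 2 alone.** Simulated bias is 0.0 and coverage 95.0%. The SE is 49 × √(2/85) = 7.52, and 7.52/6.46 = 1.16. Root-mean-square error is 6.5-6.6 mL/min for the pooled estimate across these scenarios, against 7.5 for Part 2.

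**Step 5: RRT incidence.** The dose is not chosen on RRT, so any bias comes through its correlation ρ with AUC1-7: about (30/115) × (0.846/√30) × ρ × √(p(1−p)) with equal doses. The documents give neither ρ nor the RRT rate p. Assuming ρ of 0.3-0.7 and p of 20-40%, the result is about 0.5-1.4 percentage points in favour of recAP.

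**The case against.** The strongest reply is that the selection-free number is already planned. SAP Section 8.1.1 makes the Part 2 difference and 95% interval a primary-analysis output, and Section 4 repeats the primary and key secondary analyses by part. A careful Phase 3 planner will find it. That stands, and it makes the point one of presentation. It does not remove it, because the table meant to summarise efficacy overall is specified on the other set and carries no label.

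Three stronger readings are tempting and should not be made.

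- *The pooled interval fails to cover.* Two-sided coverage is 94.6-94.9%, a negligible loss. Only the split of the misses is off.
- *The table sets a selection-adjusted p-value beside an unadjusted AUC1-7 estimate and interval.* Section 8 does not name AUC1-7, an interval or that layout. Including the primary endpoint is a reasonable inference, and 95% intervals are the SAP's default (Section 4), but both remain inferences.
- *The pooled value should be replaced throughout.* Its root-mean-square error is lower than Part 2's in every scenario, so removing it trades a small bias for a larger loss of precision. For RRT, the specified analysis uses the ITT Combined Set, and Part 2-only values in the table would disagree with it.

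It is also fair that 2.0 mL/min is the equal-dose case. Setting it against the 9.5 mL/min threshold (21%) describes only the situation where all three doses just reach 69.5. Patients recruited during the interim would dilute the bias further: with about 13 more per arm (n₂ = 98), the maximum is 7.57 × 30/128 = 1.77.

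**Conclusion.** The point holds as a reporting defect. The summary table is based on data that include those used to choose the dose, no adjustment or warning is planned, and the resulting error runs in one direction. For AUC1-7 it is about 0.7 to 2.0 mL/min. The lower 95% limit of an unadjusted pooled interval would be too high in about 3.2-4.5% of trials instead of 2.5%. The confirmatory p-value is not affected.

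This rests on AUC1-7 being one of the unnamed key endpoints, on selection by the largest Part 1 mean, and on the planning SD and means. Site effects, the DMC's safety judgement and the Emax model listed among the interim outputs are ignored. The Part 2 estimate is free of the bias provided that no patient in the ITT Part 2 Set contributed to the dose choice. For endpoints other than AUC1-7 the size cannot be derived from the documents.

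**What to change.** In the Section 8 summary table:

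- For AUC1-7, show the already planned Part 2 least squares mean difference and 95% interval (ITT Part 2 Set), identified as the selection-free effect size.
- Keep the pooled value beside it if wanted, labelled as not adjusted for dose selection.
- For RRT incidence and the other endpoints, keep the specified ITT Combined analyses and add the same label.
- List the endpoints in the table and state whether intervals are shown.

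The cost is a change to the table shell and footnotes, with no new data, model or change to the confirmatory test. The Part 2 interval is about 16% wider (SE 7.5 against 6.5 mL/min), which is the reason to show both values rather than drop the pooled one.
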